8.2.5 Physician's global assessment of disease activity (PhGADA)

The Investigator will assess the overall status of the subject with respect to the axSpA signs and symptoms and the functional capacity of the subject using a visual analog scale where 0 is "very good, asymptomatic and no limitation of normal activities" and 100 is "very poor, very severe symptoms that are intolerable, and the inability to carry out all normal activities." The data including the change from baseline at Week 48 and Week 96 will be summarized as secondary endpoints.

8.2.6 Swollen and tender joint counts

The following 44 joints are to be examined for swelling and tenderness by the Investigator, another delegated physician, or an appropriately qualified medical professional (based on local requirements) who has had documented training on how to perform these assessments correctly. Preferably the same assessor should evaluate the subject at each arthritis assessment.

- Upper body (4) – bilateral sternoclavicular and acromioclavicular joints.
- Upper extremity (26) – bilateral shoulders, elbows, wrists (includes radiocarpal, carpal, and carpometacarpal bones considered as a single unit), metacarpophalangeals (MCPs) I, II, III, IV, and V, and thumb interphalangeals (IPs), and proximal IPs (PIPs) II, III, IV, and V.
- Lower extremity (14) – bilateral knees, ankles, and metatarsophalangeals (I, II, III, IV, and V).

The assessment for swelling and tenderness is made on 44 joints from the above list. Artificial, ankylosed, and missing joints are excluded from swelling and tenderness assessments.

Each joint is scored for tenderness as follows:

0 = None (not tender)

1 = Positive (tender)

Each joint is scored for swelling as follows:

0 = None

1 = Detectable

Tender joint counts (TJC) and swollen joint counts (SJC) are calculated as the sum of tender and swollen joints, respectively, among the 44 joints. Both TJC and SJC range from 0 to 44.

If there are missing observations for tender or swollen joints then the remaining observations will be assessed and weighted by dividing by number of non-missing and then multiplying by 44 for the joint count. If a joint is not evaluable at Baseline, then that joint is set to missing throughout the study. If data for more than 50% of the joints are missing at the time of a given assessment, then no imputation will be done and the total TJC or SJC will be set to missing for that visit.

TJC summaries will be based only on those subjects with at least one tender joint at Baseline. Similarly, SJC tables will be based only on those subjects with at least one swollen joint at Baseline.

The data including the change from baseline at Week 48 and Week 96 will be summarized as secondary endpoints.

8.2.7 Patient's global assessment of disease activity (PtGADA)

For the PtGADA questionnaire, subjects will score their global assessment of their disease activity in response to the question "How active was your spondylitis on average during the last week?" using a NRS where 0 is "not active" and 10 is "very active" (van Tubergen et al, 2015). The data including the change from baseline at Week 48 and Week 96 will be summarized as secondary endpoints.

8.2.8 Total and nocturnal spinal pain

The questionnaire for pain in the spine due to AS consists of 2 questions (ie, "How much pain of your spine due to spondylitis do you have?"; and "How much pain of your spine due to spondylitis do you have at night?") (van der Heijde et al, 2005). Total and nocturnal spinal pain will be recorded based on a NRS ranging from 0 to 10, where 0 represents no pain and 10 represents most severe pain. Usually, a 10% difference (ie, a 1 point difference on a NRS ranging from 0 to 10) is considered the minimal clinically important difference used to interpret scores (Dworkin et al, 2008). The total spinal pain data including the change from baseline at Week 48 and Week 96 will be summarized as secondary endpoints.

8.2.9 Bath ankylosing spondylitis functional index (BASFI)

The BASFI contains 10 questions. The first 8 questions [REDACTED]. The final 2 questions [REDACTED]. An NRS ranging from 0 to 10 is used to answer the questions on the test. The BASFI questions can be found in appendix 16.7 of the clinical study protocol.

The mean of the 10 scales gives the BASFI score, which is a value between 0 and 10.

In case of missing answers to 1 or 2 of the single items within the BASFI questionnaire, the BASFI score will be calculated by imputing missing items with the mean of the completed items. Then, the BASFI score will be calculated as described above. If more than 2 of the items are missing, the BASFI score will be left missing.

Change from Baseline in BASFI at Week 48 and Week 96 are secondary efficacy endpoints.

8.3 Analysis of other efficacy variables

All other efficacy endpoints with exception of flare duration and severity will be tabulated at all time points acc to assessment schedule.

8.3.1 Flare assessments

For each subject in FAS, the total duration and the maximum severity of pre-study and on-study AU flares will be determined and summarized. The duration of an episode of AU flare (T_{Dur_Fl}) is calculated as follows:

$$T_{Dur_Fl} = Date_{End_Fl} - Date_{Start_Fl} + 1$$

with $Date_{End_Fl}$ and $Date_{Start_Fl}$ the end date and start date of flare, respectively. The duration of pre-study and on-study periods is defined in Section 4.2.

For the interim analysis, the pre-study period is starting 48 weeks prior to Baseline, i.e. 336 days prior to Baseline until Baseline. The on-study period for the interim analysis is starting from Baseline until week 48, i.e. until study day 336.

For the final analysis, the pre-study period is starting 24 months prior to Baseline, i.e. 730 days prior to Baseline until Baseline. The on-study period for the final analysis is starting from Baseline until week 96, i.e. until the date of the Week 96 or discontinuation visit.

The highest grade (severity) of uveitis flare across all flares per subject will be summarized. The highest grade (severity) noted during an episode of uveitis will be graded as follows: Grade 0=None; Grade 1+=Faint; Grade 2+=Moderate, iris and lens details clear; Grade 3+=Marked, iris and lens details hazy; Grade 4+=Intense, fibrin or plastic aqueous; ND=Not done or not assessed; UNK=Unknown

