9 ASSESSMENT OF EFFICACY

9.1 Assessment of primary and secondary efficacy variables

9.1.1 Assessment of AU flares

Subjects will be requested to contact an ophthalmologist when they experience an AU flare at any time during the study. The ophthalmologist will confirm the AU flare and determine the duration, severity, and treatment. The ophthalmologist will be provided with documentation to ensure all protocol-requested information is collected. The documentation will inform the ophthalmologist about the subject's study participation and the requirements.

At each site visit, the subject will be questioned on the occurrence of uveits flares since last visit. In case uveitis flares are confirmed by the subject the site will obtain the needed information from the ophthalmologist containing the diagnosis of AU, the affected eye, location of the uveitis in the affected eye, duration, severity, and treatment provided.

The following information will be collected:

- Start and end date of each AU flare (episode)
 - Start date: when subject experience first signs of the AU episode
 - End date: when treatment of the AU is stopped
- Grading
 - For uveitis flare, the highest grade noted during an episode of uveitis will be graded as follows:
 - Grade 0=None; Grade 1+=Faint; Grade 2+=Moderate, iris and lens details clear; Grade3+=Marked, iris and lens details hazy; Grade4+=Intense, fibrin or plastic aqueous; ND=Not done or not assessed; UNK=Unknown
 - For cell count, the highest cell count noted during an episode of uveitis will be graded as follows:

Grade 0=<1 cell; Grade 0.5+=1-5 cells; Grade 1+=6-15 cells; Grade 2+=16-25 cells; Grade 3+=26-50 cells; Grade 4+=>50 cells; ND=Not done or not assessed; UNK=Unknown

Treatment

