2.1.3 Other objectives

The other objectives of the study will be to assess the effect of CZP treatment on:

- Physical function
- Signs and symptoms of axSpA
 - Morning stiffness
 - Fatigue
 - Extra-articular manifestations of axSpA
- Duration and severity of AU flares

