Unless stated otherwise, all inferential statistical tests will be 2-sided and conducted at the 0.05 alpha level. Adjustment for multiplicity is described in [Section 4.5](#). P-values for secondary efficacy variables are nominal. P-values will be presented to 3 decimal places and any values below 0.001 should be displayed as “<0.001”.

All data in the database (SDTM and ADaM) will be presented in by-subject data listings, and sorted by subject number, parameter (where applicable), and visit (where applicable). For listings including subjects that were not treated, these subjects will be shown first in the listing, ordered by subject number. All listings will include repeated and unscheduled measurements. Such measurements will appear in chronological order together with the scheduled visits, i.e., a repeated measurement will appear directly after the visit and time relative to dosing, for which the repeat measurement was performed. In all the listings dates will be presented in the format ‘YYYY-MM-DD’ and times will be presented in 24h clock format as ‘hh:mm’ or ‘hh:mm:ss’ where appropriate.

All tabulations will be sorted by parameter and visit. Only scheduled visits will be included in the tabulation. Categorical data will be summarized by visit, using the number and percentage of subjects in each category. Percentages will be based on the corresponding population size (i.e., the denominator of percentages should match the sample size in the column header), unless otherwise noted via footnote in the applicable summary table. Percentages will be presented to 1 decimal place. For data points with $n=0$ (i.e., no subjects in the applicable category), no value for percentage of subjects will be displayed.

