8.1.2 Supportive and sensitivity analyses of the primary efficacy variable

The primary efficacy analysis will be repeated in the subgroup of subjects with at least 1 documented AU flare within 12 months prior to Baseline.

The AU flares as reported by the investigators, without programmatically correcting for the 3 month interval between 2 flares, will be analyzed in addition to the primary efficacy variable of protocol-defined AU flares at least 3 months apart.

The primary analysis will be repeated using the pre-study period as 96 weeks (672 days) prior to start of study medication for counting flares and as the offset, instead of 24 months. The on-study period will be the same as that used for the primary analysis.

In addition, the analysis for the full 2 years before and after study medication will be provided. The pre-study period will be the 2 years (730 days) prior to start of study medication, which will be used for counting flares and as the offset. The on-study period will be determined for whose episodes of AU flares for which the start date of flare is on or after the start date of study

medication and up to and including the SFU visit or date of last administration of study medication + 70 days.

An analysis for the first 48 weeks will also be produced. The period for pre-study will be the 12 months (365 days) prior to start of study medication, which will be used for counting flares and as the offset. An episode of AU flares will be considered on-study, if the start date of flare is on or after the start date of study medication and up to and including the Week 48 visit or discontinuation visit if prior to Week 48. The exact date of the Week 48 or discontinuation visit will be used for each subject. This analysis will also be repeated using 48 weeks (336 days) as the pre-study period for counting flares and as offset, but keeping the on-study period of 48 weeks the same (i.e. using the exact date of the Week 48 or discontinuation visit).

The primary efficacy analysis will be repeated in the subgroup of subjects excluding those with any pre-study flares with completely missing end dates in the 2 years prior to baseline. Subjects will be excluded if any of the flares that started within the 2 years prior to baseline have completely missing end dates (i.e. no day, month or year)

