8.2.1 Number of AU flares per 100 patient-years

The number of AU flares per 100 patient-years in subjects with active axSpA and a history of AU will be calculated and the corresponding 95% confidence interval for both pre-study and on-study periods. Similarly, the number of AU flares per 100 patient-years in subjects with active axSpA and at least 1 AU episode within 12 months prior Baseline, and the corresponding 95% confidence interval will be presented. This variable is also supportive of primary efficacy analysis.

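### SAP 8.3.1 summarises flare duration and severity only as an unscaled per-subject total and maximum, which measure flare burden rather than how long or how severe flares are

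*SAP*

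**What the plan says.** SAP 2.1.3 lists "Duration and severity of AU flares" among the other objectives. Section 8.3.1 gives the analysis: "For each subject in FAS, the total duration and the maximum severity of pre-study and on-study AU flares will be determined and summarized". It defines the duration of one episode as end date minus start date plus one day, but only the per-subject total is summarised. For severity, the summary is each subject's highest grade over all flares.

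The windows are set in the same section: "For the final analysis, the pre-study period is starting 24 months prior to Baseline, i.e. 730 days prior to Baseline until Baseline". The on-study window runs from Baseline to the Week 96 or discontinuation visit, so 96 × 7 = 672 days nominally, or less. For the interim analysis both windows are nominally 336 days.

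Section 8.3 states that "All other efficacy endpoints with exception of flare duration and severity will be tabulated at all time points", so 8.3.1 is the only place in the SAP text that specifies a summary of these two variables.

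Time adjustment is specified for flare counts:
- 8.1.1 has a log-time offset.
- 8.1.2 repeats the primary analysis with 672 days "prior to start of study medication for counting flares and as the offset, instead of 24 months".
- 8.2.1 gives rates: "The number of AU flares per 100 patient-years in subjects with active axSpA and a history of AU will be calculated".

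Protocol 9.1.1 collects start date, end date and highest grade for each episode. SAP 3.1 provides for listings: "All data in the database (SDTM and ADaM) will be presented in by-subject data listings".

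SAP 4.2 treats a completely missing end date differently in the two periods. Pre-study, it takes the earliest of three dates, one of which is the start date plus the subject's median flare duration; that median may include on-study flares. On-study, it takes the start of the next flare in the same eye and otherwise leaves the flare open.

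**The concern.** A sum and a maximum over a subject's flares both depend on how many flares the subject has, and the trial is planned around a halving of that number. If the primary hypothesis is true, both measures should improve whether or not treatment changes an individual flare. A report could then present a smaller on-study total, or a lower maximum grade, as shorter or milder flares when the data show only fewer.

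The unequal final windows add a smaller push in the same direction. In addition, an on-study flare left open under 4.2 gives the duration formula no end date.

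At stake is the reading of one exploratory objective.

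**Working it through.** **Inputs.** Rates of 0.292 (pre-study) and 0.146 (CZP) flares per year, average follow-up 1.5 years, two-sided alpha 0.049, 80% power and N = 86 come from SAP 2.4. The windows come from 8.3.1. Assumptions: Poisson counts, 730 pre-study days for everyone, and the same flare length and grade distribution in both periods.

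**The plan's own figure.** Signorini's formula with half the subjects in each group and b = ln 0.5:
- N = (1.969 × √4 + 0.842 × √6)² / (1.5 × 0.292 × b²) = 171.0 in total, or 85.5 per group, rounded up to 86. The stated N is reproduced, so these rates are the planning rates.

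**Expected flares per subject.**
- Pre-study: 0.292 × 730/365.25 = 0.584.
- On-study, no effect: 0.292 × 672/365.25 = 0.537.
- On-study, halved rate: 0.269.

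**Total duration, on-study/pre-study, flare-free subjects as 0.** Flare length cancels.
- No effect (window only): 672/730 = 0.92.
- Halved rate, flares unchanged: 0.50 × 0.92 = 0.46.
- Halved rate, each flare twice as long: 0.50 × 2 × 0.92 = 0.92. The total still falls.
- At the plan's 1.5-year average follow-up: window only 547.9/730 = 0.75; with the halved rate 0.375.
- A subject leaving at Week 48: window ratio 336/730 = 0.46.
- Equal 336-day windows, halved rate: 0.50.

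**Maximum grade.** If a share p of flares reaches grade 3+ or higher, the expected share of subjects whose maximum is at that level is 1 − exp(−m × p), where m is the mean number of flares. The documents give no p, so a range is shown.

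| Assumed p | Pre-study | On-study, no effect | On-study, halved rate |
|---|---|---|---|
| 10% | 5.7% | 5.2% | 2.7% |
| 30% | 16.1% | 14.9% | 7.7% |
| 50% | 25.3% | 23.6% | 12.6% |

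**What other summaries would show, with a halved rate and flares unchanged.** The per-episode duration ratio is 1.00. The flare-days per patient-year ratio is 0.50.

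**Limits of a per-episode summary.**
- Size at N = 86: 86 × 0.584 = 50.2 flares pre-study and 86 × 0.269 = 23.1 on-study.
- Precision, for lognormal independent durations with an assumed CV of 0.5 to 1.0: SD of the log = √ln(1 + CV²) = 0.472 to 0.833. SE = SD × √(1/50.2 + 1/23.1) = 0.119 to 0.209. The 95% limits on a ratio of geometric means are × or ÷ exp(1.96 × SE) = 1.26 to 1.51.
- Selection, assuming half of flares last 1 unit and half last 2 (mean 1.5), with half of all flares prevented: if 75% of those prevented are short, the remaining mean is (0.125 × 1 + 0.375 × 2)/0.5 = 1.75, ratio 1.17. If 75% are long, it is 1.25, ratio 0.83. No individual flare has changed in either case.

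**Choice of pre-study denominator.** The 8.1.1 offset starts at the first uveitis flare if that falls within two years of Baseline. If a share f of subjects is affected, with first flares spread evenly, pre-study flare-days per patient-year rise by 1/(1 − f/2): 1.05, 1.11 and 1.18 for assumed f of 10%, 20% and 30%.

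**The case against.** **Windows.** For completers the window effect is only 0.92. SAP 8.3.1 gives nominally equal windows at the interim, and 4.3 says of AU flare data that the 48-week analysis is repeated at the final, which can be read as covering duration and severity. Section 4.3 also still gives 96 weeks for both periods at the final, against 730 days in 8.3.1; if 4.3 governed, the window part would vanish for completers. This stands: the window is the minor component. The mixing with flare count remains under equal windows (ratio 0.50).

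**Recoverable from reported counts.** Mean total days divided by mean number of flares gives crude days per flare. True for duration, though the division is not prespecified and has no interval. Maximum grade cannot be unpacked this way.

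**Burden is a legitimate choice.** The objective does not say per flare, and a total over every subject avoids conditioning on having a flare. This stands, and is why both measures should stay with the right label.

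**The remedy is weak too.** A per-episode table would be small and open to selection, and the pre-study imputation in 4.2 can draw the periods together. Protocol 9.1.1 describes flares during the study; grading of pre-study flares is implied only by 8.3.1. These are fair limits. They call for caveats on the table.

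**Flare-free subjects.** Largely answered: 8.3.1 covers each FAS subject, and 3.1 bases percentages on the analysis set and requires a missing row. Whether such subjects show as Grade 0 or missing is labelling.

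**Display specifications.** SAP 4.3 refers to them and they were not available, so a per-episode table may exist there. The SAP text does not specify one.

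**Conclusion.** The point holds as a modest one. In the final analysis the total and the maximum describe burden and do not by themselves answer the duration and severity objective. At the planning rates the expected total-duration ratio is 0.46 with every flare unchanged, which is a real halving of burden (0.50) times a window effect (0.92). The share of subjects with a maximum grade of 3+ or higher roughly halves on the same basis (16.1% to 7.7% if 30% of flares reach that grade). These figures rest on the planning rates, Poisson counts and unchanged flares.

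Three stronger readings are tempting and are not supported:
- *That the plan can say nothing about flare length.* Crude days per flare can be derived from the reported totals and counts.
- *That unequal windows create most of the apparent benefit.* For completers they account for 8%, and a 48-week matched repeat can be read into 4.3.
- *That the trial's conclusion is at risk.* SAP 8 makes every analysis except the primary exploratory, and the primary count analysis has its own offset.

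This is a low-stakes improvement.

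**What to change.** In SAP 8.3.1, by period:

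1. Add a descriptive summary of duration and highest grade per flare episode, where graded, with not-done and unknown grades shown. Note that it conditions on having a flare, so treatment may change which flares are seen, and that few on-study flares are expected. Because imputed pre-study end dates may use a median that includes on-study flares, also show it for episodes with observed end dates only.
2. Report total duration as flare-days per patient-year, labelled as burden, with flare-free subjects counted as 0. State the pre-study denominator and show the result with both the 730 days and the 8.1.1 offset: the first matches the collection window, the second matches the primary model but starts its clock at a flare.
3. Truncate an on-study flare left open under 4.2 at the end of the on-study period, so that the duration formula can be computed.

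Keep the unscaled total and maximum as burden descriptors.

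The cost is minor SAP wording and programming, using data already collected; pre-study grades can be shown only as far as they were recorded. The apparent benefit on duration and severity may look smaller, and the per-episode table will be imprecise.

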8.3.2 Extra-articular assessments

Extra-articular assessments (eg, number of IBD exacerbations and number of psoriasis exacerbations) are to be performed at Screening, Baseline, Weeks 12, 24, 36, 48, 60, 72, 84, and at Completion at Week 96/WD Visit. At each visit, the number of episodes since the last visit and the number of days with IBD/psoriasis are collected. Episodes are considered equivalent to exacerbations. These data will be summarized using summary statistics for continuous variables.

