5.1 Study description

AS0007 is a multicenter, open-label, Phase 4 study to evaluate the effect of CZP on the incidence of AU flares per year in subjects with both active axSpA and a history of AU by comparing the historical AU flare rate that occurred prior to CZP treatment with the AU flare rate occurring while under CZP treatment.

The study duration from the start of treatment will be 96 weeks from Baseline onwards, and a FU Visit will be performed at Week 104, 10 weeks after the final dose. A schedule of study assessments is provided in Table 5-1.

The study includes 3 periods as follows:

Period 1 (Screening Period): 1 to 5 weeks before Baseline

Subjects will be informed about the study and sign the ICF. Eligibility will be evaluated and assessments will be performed as listed in Table 5-1. The Screening Period should be kept as short as possible but can be extended to 5 weeks if certain medications need to be washed out or to allow to obtain information from the subject's ophthalmologist. For subjects who start a prophylactic treatment for LTBI, the Screening Period can be extended up to 12 weeks (see Section 10.6.4.1).

Period 2 (Treatment Period): Week 0 to Week 96

Eligible subjects will receive a dose of CZP 400mg sc administered at Baseline, Week 2, and Week 4 followed by CZP 200mg sc Q2W (starting at Week 6 until Week 94).

All subjects will be trained at the beginning of the study on self-administration before the subjects start with self-administration (relative or caregiver may also perform the injections). The injection schedule will provide the sequence of self-administration and site visits including injection at the site.

Period 3 (FU Period): 10 weeks from the final dose of study medication received.

A Week 48 analysis will be performed after all subjects have either completed the Week 48 Visit or have prematurely withdrawn prior to the Week 48 Visit. The final analysis will be conducted at the end of the study after all study data is locked.

5.1.1 Study 3

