9.1.10 Extra-articular assessments

Extra-articular assessments (eg, number of IBD exacerbations and number of psoriasis exacerbations [in subjects with concurrent psoriasis]) are to be performed at Screening, Baseline, Weeks 12, 24, 36, 48, 60, 72, 84, and at Completion at Week 96/WD Visit.

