3.2 General study level definitions

3.2.1 Analysis time points

The study includes 3 periods as follows:

- **Period 1** (Screening Period): 1 to 5 weeks before Baseline

The pre-treatment period (Screening period) of the study is the period prior to a subject's first dose of study medication intake. This period starts at the Screening visit (week -5 to -1 day, extended to week -12 for subjects who start a prophylactic treatment for LTBI) and ends at the Baseline visit (Week 0) up to the time of first study medication administration (exclusive). Unless specific time information is available to indicate that a Screening or Baseline visit assessment was performed after a subject's first study medication administration, most assessments will be attributed to the Screening period. Exceptions to this are AEs that start on Baseline visit, as they will be attributed to the Treatment Period.

- **Period 2** (Treatment Period): Week 0 to Week 96

The treatment period begins at the Baseline visit (Week 0) at the time of first study medication administration (inclusive) and ends at Week 96/WD visit. Premature withdrawal visit assessments will be assigned to the next scheduled visit following the last visit where assessments are available. All visit measurements, even violating the visit window, will be utilized for the respective visit as long as they are in the proper sequence. Subjects will be classified as completing the study if they complete the Week 96 Visit without early withdrawal of the study. This is regardless of whether they attend the Follow-up visit.

- **Period 3** (FU Period): 10 weeks from the final dose of study medication received

The Follow-up visit will take place 10 weeks after the last dose of study medication. That is either 8 weeks after the Week 96 visit for subjects completing the study, or up to 10 weeks after the WD visit for withdrawn subjects.

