3.3 Definition of Baseline values

Unless otherwise specified, the last valid measurement before study medication administration will be utilized as Baseline value. For almost all variables, this will be the assessment made at the Baseline visit. However, for some variables, assessments may be scheduled for Screening only and not for Baseline. In this case the screening value will be utilized as baseline value. If a baseline measurement is missing, and a screening value available, the screening value will be utilized as Baseline instead. If a scheduled Baseline assessment is taken on the same day as first administration of study medication, it will be used as Baseline, irrespective of the time of the assessment relative to the first administration of study medication.

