8.2 Statistical analysis of the secondary efficacy variable(s)

Secondary and other efficacy variables will be summarized by time point including change from Baseline or shift from Baseline, with descriptive statistics. Arithmetic mean, SD, median, minimum and maximum value will be displayed for continuous variables. The secondary efficacy variables are assessed at Week 48 and Week 96. All efficacy analyses will be based on the SS or FAS as appropriate.

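### IBD and psoriasis exacerbations are raw counts over unequal windows, so change from Baseline would show apparent worsening at most on-treatment visits even with no drug effect

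*SAP*

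**What the plan says.** SAP 2.2.1.3 lists the number of IBD exacerbations and the number of psoriasis exacerbations (the latter in subjects with concurrent psoriasis) among the other efficacy variables.

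Protocol 9.1.10 sets the timing. The assessments "are to be performed at Screening, Baseline, Weeks 12, 24, 36, 48, 60, 72, 84, and at Completion at Week 96/WD Visit". The schedules of assessments show none at Weeks 2, 4 or 32, although subjects attend the site then.

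SAP 8.3.2 says what is recorded, "At each visit, the number of episodes since the last visit and the number of days with IBD/psoriasis are collected", and how it is analysed: "These data will be summarized using summary statistics for continuous variables".

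SAP 3.3 fixes Baseline: "the last valid measurement before study medication administration will be utilized as Baseline value". If that value is missing, the Screening value replaces it. Protocol 5.1 places Screening "1 to 5 weeks before Baseline". For subjects starting LTBI prophylaxis, "the Screening Period can be extended up to 12 weeks".

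The comparison with Baseline comes from general rules. SAP 8.2 states: "Secondary and other efficacy variables will be summarized by time point including change from Baseline or shift from Baseline, with descriptive statistics". SAP 3.1 applies change from Baseline to continuous data by visit, and Protocol 12.3.2 says the same for other efficacy variables. SAP 8.3 tabulates all other efficacy endpoints at every scheduled time point and exempts only flare duration and severity.

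**The concern.** A count since the previous visit grows with the time it covers. If that time is short at Baseline and long on treatment, the difference between the two mixes any drug effect with the difference in window length. A reader of the by-visit table could conclude that IBD or psoriasis worsened on CZP, or could miss a real improvement. Even without a change column, the table would set a short-window Baseline mean beside 12-week means.

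Extra-articular manifestations are among the trial's other objectives, and these counts are two of the variables that inform it. The SAP allows for observed time elsewhere: the AU flare model has a log-time offset (8.1.1), AU flares are reported per 100 patient-years (8.2.1), and adverse events have exposure-adjusted rates (10.2). These counts have no such provision.

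**Working it through.** The documents give no figure for this endpoint, so there is nothing to reproduce. The check asks what the planned comparison shows when CZP does nothing.

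**Inputs.** The Baseline window is 1 to 5 weeks, or up to 12 weeks with LTBI prophylaxis (Protocol 5.1). On-treatment assessments are 12 weeks apart (Protocol 9.1.10). If the last visit means any site visit, Week 12 looks back to Week 4 (8 weeks) and Week 36 looks back to Week 32 (4 weeks). The other six on-treatment assessments (Weeks 24, 48, 60, 72, 84 and 96) still look back 12 weeks. The documents give no exacerbation rate, so 0.5, 1 and 2 per patient-year are assumed.

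**Formulas.** With a constant rate *r* per year, the expected count is *r* × window / 52.18. So:
- ratio = on-treatment window / Baseline window, which does not depend on *r*;
- expected change = *r* × (on-treatment window − Baseline window) / 52.18.

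**Results** (ratio, then expected change per affected subject at *r* = 1; the change halves at 0.5 and doubles at 2):

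| Baseline window | 12-week visit | Week 12, if 8 weeks | Week 36, if 4 weeks |
|---|---|---|---|
| 1 week | 12.0; +0.211 | 8.0; +0.134 | 4.0; +0.057 |
| 3 weeks | 4.0; +0.172 | 2.67; +0.096 | 1.33; +0.019 |
| 5 weeks | 2.4; +0.134 | 1.6; +0.057 | 0.8; −0.019 |
| 12 weeks (LTBI) | 1.0; 0.000 | 0.67; −0.077 | 0.33; −0.153 |

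For example, with a 3-week Baseline window at *r* = 1, the expected counts are 3/52.18 = 0.057 at Baseline and 12/52.18 = 0.230 at a 12-week visit.

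**Effect needed to show no change.** At a 12-week visit the true rate ratio would have to be 5/12 = 0.42 (a 58% reduction) after a 5-week Baseline window, or 1/12 = 0.08 (a 92% reduction) after a 1-week window.

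**Simulation.** One million subjects were simulated with Poisson counts, a Baseline window uniform on 1 to 5 weeks and a 12-week on-treatment window. The mean change was +0.09, +0.17 and +0.34 at rates 0.5, 1 and 2. At rate 1, 19.5% of subjects had a higher count than at Baseline and 4.4% a lower one. When total episodes were divided by total observed time, the change was within 0.01 per patient-year of zero at all three rates.

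**Why the definition matters for a rate too.** Under the any-site-visit reading, the on-treatment windows add to 8 + 12 + 4 + 5 × 12 = 84 weeks, not 96. Weeks 0 to 4 and 24 to 32 would not be covered, and dividing by 96 weeks would understate the rate by 1 − 84/96 = 12.5%.

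**The case against.** The strongest reply is that SAP 8.3.2 does not ask for change from Baseline. The variable list names most other measures as changes from Baseline but these two simply as numbers, and the table layout rests on display specifications outside these documents. This stands in part: a reader might infer that the change is specified for this variable, and it is not. But the general rules do reach it, SAP 8.3 does not exempt it, and a programmer following the SAP would produce it.

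A reader might also infer that every on-treatment visit must look worse than Baseline. The documents do not support that. If the last visit means any site visit, the ratio at Week 36 runs from 4.0 down to 0.8. A 12-week LTBI screening gives a ratio of 1.0 at a 12-week visit. Early withdrawal visits, which SAP 3.2.1 and 4.2 assign to the next scheduled visit, bring shorter windows into the 12-week columns.

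Similarly, it is tempting to say that substituting the Screening value for a missing Baseline reverses the bias. Protocol 8.1 does not state a look-back at Screening, where there is no previous visit, and the case report form is not available. The direction is unknown. Nor is it certain that the number of days shares the same window as the episodes.

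Finally, the absolute differences are small, and zeros from subjects without the condition would shrink the tabulated means further, though not the ratios. All non-primary analyses are exploratory (SAP 8), and no test or decision rests on these counts. That limits the importance of the point but does not remove the defect.

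**Conclusion.** The point holds in limited form. The counts cover unequal windows, the general rules call for change from Baseline, and nothing adjusts for time. With a constant, non-zero exacerbation rate and the usual 1 to 5 week Screening window, the expected count at 12-week visits is 2.4 to 12 times the Baseline count. Those ratios rest only on the schedule; the absolute changes rest on assumed rates. The apparent worsening is an expectation, applies at most rather than all on-treatment visits, and depends at Weeks 12 and 36 on what the last visit means.

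This is worth correcting because the table could mislead about an objective of the study. It does not touch the primary analysis, which allows for observed time through its offset.

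**What to change.** In SAP 8.3.2:

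- Define the look-back window for episodes, at Screening as well as later, and state whether it runs from the last extra-articular assessment or from the last site visit.
- Exempt these counts from the change-from-Baseline rule.
- Do not substitute the Screening value for a missing Baseline unless its look-back is defined.
- Report on-study exacerbations as total episodes divided by total observed time, per 100 patient-years, with the denominator matching the defined windows.
- If a pre-treatment figure is shown, give it as a rate over its own observed time with a confidence interval, and note that it is imprecise.
- Treat days with IBD or psoriasis the same way if they share that window.

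Showing IBD results in subjects with concurrent IBD is optional. For psoriasis, that restriction is already in the variable as listed in SAP 2.2.1.3, and 8.3.2 should match it.

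The cost is SAP wording and one table shell, since visit dates and counts are already collected. The drawback is little pre-treatment information: with a 3-week window, 86 subjects give about 86 × 3/52 ≈ 5 patient-years if all had the condition, and about 0.5 if an assumed 10% did. The on-study figure would be 86 × 1.5 = 129 patient-years if all had the condition, at the average follow-up in SAP 2.4.
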